## PROTOCOL AMENDMENT HISTORY TABLE

Protocol # Version Date	Section (Section & page #)	Language Added/Revised/Deleted	Rationale
V1.1	Header	IRB number added	
	Section 9.3	A telephone call will be made by an authorized study research staff member to assess if the subject was readmitted within 30 days of discharge.	Detail added
V1.2	Section 5.2.3, 5.2.5	Adding St. George questionnaire-short version to enrollment. And adding short version term to 5.2.5 Questionnaire name.	
Amendment 1 9 December 2022	Section 4 b i Page 20	Inclusion criteria  Diagnosis of COPD  inspiratory flow rate	Diagnosis of COPD (per investigator's discretion by prior spirometry results or by spirometry assessment at screening visit)  Acronym has been added (PIFR)
Amendment 1 9 December 2022	Section 5.2.2, section 5.2.3 Page 23-22	Change in the procedures during the screening visit section and enrollment section	The procedures during the screening visit will include: 

1. Assignment of screening number

2. Spirometry (FEV1, FVC, FEV1/FVC)

3. Demographics

4. Medical History

5. Decision by investigator to enroll subject or to

			declare screen failure.
Amendment 1 9 December 2022	Section 5.2.4 Page 24	Change in the time of treatment administration	Treatments will be administered by a respiratory therapist daily in the morning between 06:00 AM and 12:00 PM.
Amendment 1 9 December 2022	Section 5.2.5 Page 25	A schedule a follow-up with the subject in the research clinic	To obtain the missed assessments.
Amendment 1 9 December 2022	Section 16.1 Pages 37-38	Gilead Science is deleted	The sponsor is GlaxoSmithKline plc. (GSK)
Amendment 1 9 December 2022	Section 16.2 Page 39	FDA Form 1572 is deleted from the Essential Documents list	Invalid
Amendment 2 8 March 2023	Section 1, Page 14 Section 4, Page 20 Section 8.7, Page 32	9-month enrollment duration removed	Updated enrollment timeline.

## LIST OF ABBREVIATIONS

Abbreviation	Term
AE	Adverse event
Ab	Antibody
Ag	Antigen
CRF	Case report form
FDA	Food and Drug Administration
HIPAA	Health Insurance Portability and Accountability Act of 1996
IHC	Immunohistochemistry
IL-1R	Interleukin-1 Receptor
IR	Increased risk
IRB	Institutional Review Board
ITT	Intent to treat
IV	Intravenous
PHI	Protected health information
PI	Principal Investigator
PRN	Pro re nata-as need arises
SAE	Serious adverse event
SOP	Standard operating procedure

## 1. SYNOPSIS

Summary/Rational:	This phase IV, post market approval single-center, open-label study will be used evaluate to a more standardized open-label protocol which would allow for a more accurate assessment of intervention outcomes when a combination LABA/LAMA/ICS inhaler is used as the primary scheduled daily inhaled therapy.
Study Objectives:	
Primary objective:
 

1. To establish the requirements for PRN respiratory therapy treatments in patients hospitalized with the diagnosis of COPD exacerbation receiving once-daily ICS/LABA/LAMA (fluticasone furoate/umeclidinium/vilanterol) therapy.

 
Secondary objectives:
 

1. To measure the distribution of inspiratory flow rates with an InCheck Dial device set on measuring PIF using the medium low resistance setting in patients admitted with COPD exacerbations at Baylor University Medical Center, Dallas TX at the time of enrollment and day of discharge

2. To determine the hospital length of stay for patients admitted with the diagnosis of COPD exacerbation

3. To monitor and report any side effects from using once-daily ICS/LABA/LAMA or PRN therapy.

4. To evaluate the transition of care in delivering respiratory therapy medications from hospital to home

5. To compare the number of PRN treatments, length of hospital stay, and rate of readmissions with findings in a previously

	
analyzed historical cohort of 60 patients in our healthcare system.
 
Exploratory Objectives
 
To determine the cost of respiratory care for patients hospitalized with the diagnosis of COPD exacerbation.

Study Design:	Phase IV, post market approval, single-center, open-label study
Number of Subjects:	Up to 120 subjects will be enrolled out of which approximately 80 will be TRELEGY ELLIPTA Treated Subjects; this allows for an anticipated acceptance rate of 2/3
Inclusion Criteria:	
A patient will be eligible for inclusion in this study if he or she meets all the following criteria:
 

1. Willing and capable of providing written informed consent.

2. Subjects aged 18 years or older at time of enrollment

3. Diagnosis of COPD with or without asthma for <math>\geq 12</math> months

4. Hospitalized <math>\leq 24</math> hours prior to enrollment and currently hospitalized for COPD exacerbation with or without asthma.

5. Able to properly use the Ellipta medication delivery device.

6. Able to generate <math>\geq 30</math> L/min inspiratory flow at screening, measured with an InCheck DIAL adjusted to medium low resistance, to document a subject's ability to

	effectively inhale medication delivered via an Ellipta device.
Exclusion Criteria:	

1. Clinically significant lung disease other than COPD with or without asthma

2. Positive SARS-CoV-2 test at the time of ED or hospital admission, or any time between admission and enrollment.

3. History of severe hypersensitivity to milk proteins or demonstrated hypersensitivity to fluticasone furoate, umeclidinium, vilanterol, or any of the excipients

4. Unable to perform inspiratory flow or spirometry procedures.

5. Critically ill patients, or patients with rapidly deteriorating or life-threatening episodes of COPD or asthma including:

• Patients in critical care unit or transferred from critical care unit.

○ Patients who are transferred to critical care after enrollment will be withdrawn from the study and continue to receive care according to institutional standard practice.

• Patients who initiate Bilevel Positive Airway Pressure (BiPAP) after hospitalization.

○ Patients who use BiPAP at baseline (prior to COPD exacerbation) may be included if BiPAP settings remain consistent with pre-exacerbation settings. Patients will be withdrawn if BiPAP settings are changed after enrollment.

6. Pregnant or lactating women or women of child-bearing potential (WOCBP). Women must meet the non-productive potential definition below to be eligible.

➤ Non-reproductive potential is defined as:

- Pre-menopausal females with one of the following:
  - Documented tubal ligation.
  - Documented hysteroscopic tubal occlusion procedure with follow-up confirmation of bilateral tubal ligation.
  - Hysterectomy.
  - Documented Bilateral Oophorectomy.
- Postmenopausal defined as 12 months of spontaneous amenorrhea with an appropriate clinical profile (e.g., age appropriate, >45 years, in the absence of hormone replacement therapy). In questionable cases for women <60 years of age, a blood sample with simultaneous follicle stimulating hormone and estradiol falling into the central laboratory's postmenopausal reference range is confirmatory. Females under 60 years of age, who are on HRT and whose menopausal status is in doubt, are required to use a highly effective method to avoid pregnancy if they wish to continue their HRT during the study. Otherwise, they must discontinue HRT to allow confirmation of postmenopausal status prior to study enrolment. For most forms of HRT, at least 2 to 4 weeks will elapse between the cessation of therapy and the blood draw; this interval depends on the type and dosage of HRT. Following confirmation of their post-menopausal status, subjects can resume use of HRT during

	the study without use of a highly effective method to avoid pregnancy.
Sponsor:	GlaxoSmithKline plc. (GSK)-Only provide the drug.  Baylor Scott and White Research Institute (BSWRI)
Principal Investigators:	[name]
Primary Study Site/Data Center:	Annette C. & Harold C. Simmons Transplant Institute  [name]  [contact]  [contact]
Medication:	TRELEGY ELLIPTA (fluticasone furoate 100 mcg, umeclidinium 62.5 mcg, and vilanterol 25 mcg inhalation powder)
Medication Delivery Device:	ELLIPTA

Efficacy Assessments:	

➤ Number of in-hospital PRN respiratory therapy treatments with PRN nebulized albuterol 2.5mg.

➤ Time in between PRN respiratory therapy.

➤ Change in respiratory inspiratory flow rate measured by InCheck DIAL at medium resistance from baseline to discharge.

➤ Length of stay.

➤ At-home drug compliance.

➤ 30-day re-admissions (all-cause and COPD exacerbation), 30-day survival, cost of in-hospital respiratory therapy, response to a patient satisfaction questionnaire (QOL questionnaire).

Safety Assessments:	

• Vital signs and vital status.

• Concomitant medication use.

• Reporting of adverse events.

• Pregnancy test (women of childbearing potential).

## 2. OBJECTIVES & ENDPOINTS

### a. Primary Objective

1. To establish the requirements for PRN respiratory therapy treatments in patients hospitalized with the diagnosis of COPD exacerbation receiving once-daily ICS/LABA/LAMA (fluticasone furoate/umeclidinium/vilanterol) therapy.

### b. Secondary Objectives

1. To measure the distribution of inspiratory flow rates with an InCheck Dial device set on measuring PIF using the medium low resistance setting in patients admitted with COPD exacerbations at Baylor University Medical Center, Dallas TX at the time of enrollment and day of discharge.
2. To determine the hospital length of stay for patients admitted with the diagnosis of COPD exacerbation.
3. To monitor and report any side effects from using once-daily ICS/LABA/LAMA or PRN therapy.
4. To evaluate the transition of care in delivering respiratory therapy medications from hospital to home.
5. To compare the number of PRN treatments, length of hospital stay, and rate of readmissions with findings in a previously analyzed historical cohort of 60 patients in our healthcare system.

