**b. Eligibility Criteria**

**i. Inclusion Criteria**

- a. Willing and capable of providing written informed consent.
- b. Subjects aged 18 years or older at time of enrollment.
- c. Diagnosis of COPD (per investigator's discretion by prior spirometry results or by spirometry assessment at screening visit) with or without asthma for  $\geq 12$  months.
- d. Hospitalized  $\leq 24$  hours prior to enrollment and currently hospitalized for COPD exacerbation with or without asthma.
- e. Able to properly use the Ellipta medication delivery device.
- f. Able to generate  $\geq 30$  L/min inspiratory flow rate (PIFR) at screening, measured with an InCheck DIAL adjusted to medium low resistance, to document a subject's ability to effectively inhale medication delivered via an Ellipta device.

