**ii. Exclusion Criteria**

- a. Clinically significant lung disease other than COPD with or without asthma.
- b. Positive SARS-CoV-2 test at the time of ED or hospital admission, or any time between admission and enrollment.
- c. History of severe hypersensitivity to milk proteins or demonstrated hypersensitivity to fluticasone furoate, umeclidinium, vilanterol, or any of the excipients.
- d. Unable to perform inspiratory flow or spirometry procedures.
- e. Critically ill patients, or patients with rapidly deteriorating or life-threatening episodes of COPD or asthma including:
  - Patients in critical care unit, or transferred from critical care unit.

- Patients who are transferred to critical care after enrollment will be withdrawn from the study and continue to receive care according to institutional standard practice.
- Patients who initiate Bilevel Positive Airway Pressure (BiPAP) after hospitalization.
  - Patients who use BiPAP at baseline (prior to COPD exacerbation) may be included if BiPAP settings remain consistent with pre-exacerbation settings. Patients will be withdrawn if BiPAP settings are changed after enrollment.

f. Pregnant or lactating women or women of child-bearing potential (WOCBP). Women must meet the non-productive potential definition below to be eligible.

➤ Non-reproductive potential is defined as:

- Pre-menopausal females with one of the following:
  - Documented tubal ligation.
  - Documented hysteroscopic tubal occlusion procedure with follow-up confirmation of bilateral tubal ligation.
  - Hysterectomy.
  - Documented Bilateral Oophorectomy.
- Postmenopausal defined as 12 months of spontaneous amenorrhea with an appropriate clinical profile (e.g., age appropriate, >45 years, in the absence of hormone replacement therapy). In questionable cases for women <60 years of age, a blood sample with simultaneous follicle stimulating hormone and estradiol falling into the central laboratory's postmenopausal reference range is confirmatory. Females under 60 years of age, who are on HRT and whose menopausal status is in doubt, are required to use a highly effective method to avoid pregnancy if they wish to continue their HRT during the study. Otherwise, they must discontinue HRT to allow confirmation of postmenopausal status prior to study enrolment. For most forms of HRT, at

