#### Assessments and procedures at screening

- Informed consent
- Assignment of screening number
- Inspiratory Flow Rate (PIFR) evaluation, with InCheck DIAL device set to measure medium low resistance. The best of 3 maximum inspiratory flow measurements, taken from RV will be recorded.
- Spirometry (FEV1, FVC, FEV1/FVC)
- Inclusion/Exclusion Criteria
- Demographics
- Medical History
- Decision by investigator to enroll subject or to declare screen failure.

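### Baseline inspiratory flow will be described only in patients selected for reaching 30 L/min, so secondary objective 1 cannot show how many admitted patients fall below that level

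*Combined protocol and SAP*

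**What the plan says.** Section 2.b, objective 1 (repeated in the synopsis), sets out "To measure the distribution of inspiratory flow rates with an InCheck Dial device". The population it names is COPD-exacerbation admissions to the study hospital, the device setting is medium low, and the two time points are given as "at the time of enrollment and day of discharge".

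Section 4.b.i, item f, requires at least 30 "L/min inspiratory flow rate (PIFR) at screening, measured with an InCheck DIAL adjusted to medium low resistance". Its stated purpose is to document that the patient can inhale effectively through the Ellipta device. Section 4.b.ii, item d, excludes anyone "Unable to perform inspiratory flow or spirometry procedures". Item e excludes "Critically ill patients, or patients with rapidly deteriorating or life-threatening episodes of COPD or asthma including" several listed groups.

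Section 5.2.2 lists consent, then the peak inspiratory flow rate (PIFR; best of three efforts, to be recorded), and ends with "Decision by investigator to enroll subject or to declare screen failure". Section 5.2.3 lists no separate flow measurement at enrollment, so the screening reading is the only candidate baseline.

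For analysis, section 8.7.a and section 8.7.d name the change in flow from baseline to discharge, with 8.7.d comparing it by 30-day readmission status. Section 9 (statistical analysis) adds generic summaries: mean and SD, or median and quartiles. Nothing says that readings from screen failures will be tabulated, and nothing limits objective 1 to patients at or above 30 L/min.

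**The concern.** The variable to be described is also the variable used to select. Whatever the true share of admitted patients below 30 L/min, it is 0% among eligible enrolled patients at baseline. A mean, SD or set of quartiles from the enrolled group then describes those who passed the threshold, while the objective names admitted patients.

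This matters because the protocol itself treats 30 L/min as the level that shows a patient can use the inhaler, and section 3.c proposes that inhaler as the main scheduled inpatient therapy. How many admitted patients reach that level is a natural use of objective 1. The enrolled-only baseline data cannot answer it.

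**Working it through.** **Inputs from the documents.** Threshold 30 L/min (4.b.i, item f); device setting medium low for both the objective and the threshold (2.b, 4.b.i); planned enrollment 80 from 120 approached, acceptance 2/3 (4.a). No PIFR mean, SD or expected share below 30 is given.

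**The plan's own figure.** 120 × 2/3 = 80, which reproduces. The point does not depend on it.

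**What follows without assumptions.** Baseline PIFR in enrolled patients is PIFR given PIFR ≥ 30. The share below 30 in that group is 0 by definition, so it carries no information on the share among admissions.

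**Size, under assumed values.** Let PIFR be normal with mean μ and SD σ, and a = (30 − μ)/σ.

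- Share below 30: p = Φ(a)
- λ = φ(a)/(1 − Φ(a))
- Mean after truncation: μ + σλ
- SD after truncation: σ√(1 + aλ − λ²)
- 5th percentile after truncation: μ + σΦ⁻¹(p + 0.05(1 − p))

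Worked case, μ = 50 and σ = 20: a = −1, p = 0.159, λ = 0.2420/0.8413 = 0.288. The mean is 50 + 20 × 0.288 = 55.8. The SD is 20√(1 − 0.288 − 0.083) = 15.9.

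| Assumed mean, SD | Below 30 | Truncated mean (shift) | Truncated SD | 5th percentile: full → truncated |
|---|---|---|---|---|
| 40, 15 | 25.2% | 46.4 (+6.4) | 10.9 | 15.3 → 31.7 |
| 40, 20 | 30.9% | 50.2 (+10.2) | 13.9 | 7.1 → 31.9 |
| 50, 15 | 9.1% | 52.7 (+2.7) | 12.8 | 25.3 → 33.6 |
| 50, 20 | 15.9% | 55.8 (+5.8) | 15.9 | 17.1 → 33.2 |
| 60, 15 | 2.3% | 60.8 (+0.8) | 14.1 | 35.3 → 38.0 |
| 60, 20 | 6.7% | 62.8 (+2.8) | 17.6 | 27.1 → 35.8 |
| 70, 15 | 0.4% | 70.2 (+0.2) | 14.8 | 45.3 → 45.8 |
| 70, 20 | 2.3% | 71.1 (+1.1) | 18.8 | 37.1 → 40.7 |

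The normal model is rough in the worst row: with mean 40 and SD 20 it puts Φ(−2) = 2.3% of patients below zero.

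**Screening load.** To enroll 80 when a share p fails the threshold, 80/(1 − p) patients must be measured. That is about 80 at p = 0.4% and 116 at p = 30.9%.

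**Discharge.** No threshold applies there. A simulation of baseline and discharge values as bivariate normal (mean 50, SD 20 at both times, so no average change), keeping only baseline ≥ 30, puts 10.2% of enrolled patients below 30 at discharge with correlation 0.6 and 7.3% with correlation 0.8. The figure for all patients is 15.9%. The low tail is thinned but still present.

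**The case against.** Objective 1 can be read more narrowly. It refers to the time of enrollment, which only enrolled patients have. The protocol also describes its population as admitted or hospitalized patients in the primary objective, the length-of-stay objective and the cost objective, all of which are measured in enrolled patients. On that reading the defect is loose wording. This has force, but nothing in the documents states the restriction, and stating it is part of the fix.

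Several stronger readings are tempting, and the documents do not support them:

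- A reader might infer that the whole objective is truncated. Only baseline is; an enrolled patient may read below 30 at discharge.
- A reader might infer that the plan will publish a zero share below 30. No section plans to report that share; the planned outputs are generic summaries and the change from baseline.
- A reader might infer that the bias is large. With an assumed mean of 70 it is close to nil, and the documents give nothing to choose between the rows of the table.
- A reader might infer that the missing values are all in hand. Section 5.2.1 has the team check all criteria before consent. Section 4.a expects a third of those approached, 40 of 120, not to accept. Section 4.b.ii excludes critically ill, new-BiPAP and SARS-CoV-2-positive patients. Section 5.2.2 is a bulleted list and does not expressly fix the order of its steps. Consented screen failures recover only part of the low tail.

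The 30 L/min rule has a stated purpose and is not in question here.

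**Conclusion.** The point holds for scope and reporting. Objective 1 names admitted patients, while eligibility truncates the baseline distribution at 30 L/min, and no section either tabulates screen failures or narrows the objective. That conclusion rests on the text alone.

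The size rests on assumptions. Over assumed normal means of 40 to 70 and SDs of 15 to 20 L/min, the lost share runs from 0.4% to 31% and the upward shift in the mean from negligible (0.2) to more than 6 L/min (10.2 at the extreme). This is a descriptive secondary objective and the primary endpoint is untouched. A change is still worth making, because the readings needed for a better answer should largely be collected already.

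**What to change.** 1. In section 5.2.2, state that the screening PIFR is taken before the enrollment decision, and keep it on the CRF for every consented and screened patient, including screen failures.
2. In section 8.7.d, add a table for all screened patients: number consented, number measured, the PIFR distribution, number and percent below 30 L/min, and number unable to perform. Count inability to do the flow test separately from inability to do spirometry, since exclusion d combines them.
3. Report enrolled-only baseline, discharge and change results separately. State in objective 1 (section 2.b and synopsis) that these apply to enrolled patients with screening PIFR of at least 30 L/min.
4. State that patients excluded at pre-screening or declining consent are unmeasured, so the all-screened distribution does not represent all admissions.
5. Reconcile the device setting before comparing time points. It is medium low in sections 2.b, 4.b.i, 5.2.2 and 8.7.a, but medium in section 5.2.5, section 8.2 and the synopsis efficacy assessments.

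The cost of the first four items is CRF retention, one table and some wording, with no new procedure or visit. The drawback is that the all-screened and discharge results describe different sets of patients. Making only the wording change in item 3 would remove the mismatch more cheaply, but would give up the information on patients below 30 L/min.

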### c. Exploratory Objectives

To determine the cost of respiratory care for patients hospitalized with the diagnosis of COPD exacerbation.

### d. Study Endpoints

To attain these objectives, the following study endpoints will be evaluated. Primary and secondary endpoints include the number of in-hospital PRN respiratory therapy treatments, time in between PRN respiratory therapy, change in peak inspiratory flow rate from baseline to discharge, length of stay, at-home drug compliance, 30-day re-admissions (all-cause and respiratory), 30-day survival, cost of respiratory therapy, QOL score, and safety measures (AEs and SAEs; Section 5). See section 8.7 on analytical methods to evaluate these endpoints.

### 3. BACKGROUND

#### a. Disease

The disease under study is Chronic Obstructive Pulmonary Disease (COPD), a group of progressive chronic inflammatory diseases that cause obstruction of airflow in the lungs. COPD affects 16 million people in the United States, and its death rate is approximately 40 per 100,000. Symptoms include breathing difficulty, cough, mucus/sputum production, and wheezing. The main cause of COPD in the United States is tobacco smoking. COPD may co-occur with asthma.

#### b. Therapy/Agent

TRELEGY ELLIPTA is supplied as a disposable light grey and beige plastic inhaler containing 2 foil strips, each with 30 blisters. One strip contains fluticasone furoate (100 mcg per blister), and the other strip contains a blend of umeclidinium and vilanterol (62.5 mcg and 25 mcg per blister, respectively). A blister from each strip is used to create one dose. The inhaler is packaged within a moisture-protective foil tray with a desiccant and a peelable lid.

It will be stored at room temperature between 68°F and 77°F (20°C and 25°C); excursions permitted from 59°F to 86°F (15°C to 30°C). It will be stored in a dry place away from direct heat or sunlight.

Subjects will be given TRELEGY ELLIPTA once daily at the same time every day ( $\pm$  2 hours). TRELEGY ELLIPTA will be initiated the morning of enrollment if feasible, or the morning following hospital enrollment otherwise. It will be administered as 1 inhalation by the orally inhaled route only.

*Although FDA approved, TRELEGY ELLIPTA is seldom prescribed to hospitalized COPD patients by treating physicians. Study participants will be consented prior to being prescribed TRELEGY ELLIPTA as part of this study.*

